10.4.2 Allergic Skin Responses

Allergen sites will be examined for the presence of erythema, infiltration, papules, discrete vesicles and bullous reactions and scored as follows: (-) negative, (1+) weak positive reaction, (2+) strong positive reaction, and (3+) extreme positive reaction.

All reactions (scores of 1+, 2+ or 3+) will be categorized as either late or persistent. Persistent reactions will be further clarified as either persistent-healing or persistent-escalating.

Definitions:

Late Reaction: A reaction that initially appears at day 7-14 after application of panels.

Persistent Reaction: A reaction that initially appears at day 2-4 and persists through day 7-21 or beyond.

Persistent-Healing: A persistent reaction that has not worsened since the previous evaluation, remains the same or appears to be healing.

Persistent-Escalating: A persistent reaction that has worsened since the previous evaluation

Subject-reported adverse events, worsening of a pre-existing condition/disease/symptom or changes to concomitant medications will be recorded.

De-identified photographs of site reactions may be taken at the discretion of the Investigator and will not be reviewed or collected by the study sponsor.

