10.5 Visit 6: Day 19-23

The investigative site will phone the subject to determine if there are any unresolved tape, polyester chip or allergen reactions at the test sites. If the subject reports no remaining reactions, the Investigator may choose at this point to complete the visit over the telephone.

- If the visit is conducted over the telephone all visit related paperwork including adverse events and/or changes to concomitant medications will be recorded.

Should the Investigator elect to see the subject in the office, the following procedures will be performed:

- Unresolved tape and or polyester chip induced irritation will be evaluated.
- Sites will be examined for the presence of erythema, infiltration, papules, discrete vesicles and bullous reactions and scored as follows: (-) negative, (1+) weak positive reaction, (2+) strong positive reaction, and (3+) extreme positive reaction.
- All reactions (scores of 1+, 2+ or 3+) will be categorized as either late or persistent. Late reactions are defined as reactions that initially occur at 7-10 days after application of the panels. Persistent reactions are defined as reactions that appear at day 2-4 and persist through day 7-21. Persistent reactions will be clarified as either persistent-healing or persistent-escalating. If a persistent-escalating reaction is noted at Visit 6, the investigator will determine required follow up action.
- Subject-reported adverse events, worsening of a pre-existing condition/disease/symptom or changes to concomitant medications will be recorded.
- De-identified photographs of site reactions may be taken at the discretion of the Investigator and will not be reviewed or collected by the study sponsor.

10.6 Post Visit 6

The Investigator will:

1. Evaluate tape or polyester chip induced irritation that increased in severity or persisted beyond visit 3. A potential allergic response may be considered if the skin response is consistent with criteria used to score 1+, 2+ or 3+ positive skin reactions according to standard patch testing guidelines established by the International Contact Dermatitis Research Group. The skin reaction must present with:
 - Palpable erythema, moderate edema or infiltrate, possibly few papules, no vesicles. Weak reaction (Score of 1+).
 - Strong infiltrate, numerous papules, possibly few vesicles present. Strong reaction (Score of 2+).
 - Coalescing vesicles, bullae or ulceration. Extreme reaction (Score of 3+).

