13.6 Relationship

The investigator will provide an assessment of causal relationship to the study product. The causality assessment must be recorded on the appropriate AE reporting page of the subject's data collection form. Relationship will be classified according to the following criteria:

Not Related	No association to the test drug. Related to other etiologies such as concomitant medications or conditions or subject's known clinical state. (An unrelated illness, including the worsening of a pre-existing illness, injury or accident).
Possibly Related	Uncertain association. Other etiologies are also possible.
Definitely Related	Clear-cut association with improvement upon withdrawal of the test drug. Not reasonably explained by the subject's known clinical state but not an anticipated event.

Adverse events that are to be reported as having a relationship with the study patch test panels include but are not limited to:

- A severe reaction to the test tape adhesive or allergen patch that either causes the subject to remove the panels prior to the 48 hour return visit or is determined by the investigator to be significantly greater in severity than expected or as described in the Investigator's Brochure.
- Any persistent, escalating, positive patch test reaction at the test site lasting beyond the day 21 evaluation that the investigator determines is severe.

- Any characteristic associated with a late or persistent reaction (i.e. hyper-pigmentation, hypo-pigmentation, pruritus or other) at the test site lasting beyond the day 21 evaluation that the investigator determines is severe.
- **Hyperpigmentation:** The darkening of an area of the skin caused by an excess of pigment in a tissue as opposed to an erythematic response.
- **Hypopigmentation:** The loss of skin color caused by melanocyte or melanin depletion, or a decrease in the amino acid tyrosine, which is used by melanocytes to make melanin.
- **Pruritus:** Itching
- Any of the following reactions:
- **Active Sensitization:** A positive reaction initially appearing at approximately 21 days after application. Sensitization may be confirmed if a positive reaction were to appear at 3-4 days after a repeated application of the allergen at a naïve test site.

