4.2 Secondary Endpoint (Safety)

Determination of allergen safety:

- Frequency of tape and polyester chip induced irritation or allergic reactions at Visits 2 through 6.
- Frequency of subject reported sensations of itching and/or burning for each allergen panel at patch removal.
- Frequency of positive (1+, 2+, 3+) skin reactions for each investigational and reference allergen dose at each post removal visit and overall.

STATISTICAL ANALYSIS PLAN

Date : 30 NOV 19

Version: 01

Product Name:

Sponsor Study No.: SP 14 8MP 201 Metal Allergen Epicutaneous Patch

- Frequency of negative, doubtful, irritant, late and persistent skin responses for each investigational and reference allergen dose at each post removal visit (late and persistent reactions at visits 4, 5 and 6 only).
- Frequency of all adverse events. Documentation for all local and systemic adverse reactions classified by the investigator as possibly or definitely related to the study product (e.g., erythema, hyperpigmentation, hypo-pigmentation, skin thinning or dermatitis flare) will include grade (mild, moderate or severe) and time point (clinic visit).

5. Statistical Considerations

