5.2 Derived Variable

- AE duration = AE Stop Date – AE Start Date +1
- The Skin score at visit 4, 5 and 6 are positive (1+, 2+ or 3+) and visit 3 are doubtful or irritant then it will be considered as Positive (1+) at visit 3.

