6.2 Secondary Endpoint Analysis

Frequency and percentage analysis will be carried out for below mentioned endpoints for investigational and reference allergen to obtain the safety of allergen.

Determination of allergen safety:

- Frequency of tape and polyester chip induced irritation or allergic reactions at Visits 2 through 6.
- Frequency of subject reported sensations of itching and/or burning for each allergen panel at patch removal.
- Frequency of positive (1+, 2+, 3+) skin reaction will be tabulated for the each investigational and reference allergen dose tested.
- Frequency of negative, doubtful, irritant, late and persistent skin responses for each investigational and reference allergen dose at each post removal visit (late and persistent reactions at visits 4, 5 and 6 only).
- Frequency of all adverse events. This will be brief in the section 6.2.1.

STATISTICAL ANALYSIS PLAN

Date : 30 NOV 19

Version: 01

Product Name:

Sponsor Study No.: SP 14 8MP 201 Metal Allergen Epicutaneous Patch

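### Late and persistent reaction counts are a planned safety result, but the protocol gives two windows for late, has no class for onset at Visit 6, and the SAP settles neither

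*Protocol*

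**What the plan says.** The result is planned in Protocol 7.2 and again in SAP 4.2: "Frequency of negative, doubtful, irritant, late and persistent skin responses for each investigational and reference allergen dose at each post removal visit". SAP 6.2 repeats it and limits two of the categories: "late and persistent reactions at visits 4, 5 and 6 only". The planned analysis is frequencies and percentages.

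The protocol body defines late twice. Section 10.4.2, for Visits 4 and 5, has "Late Reaction: A reaction that initially appears at day 7-14 after application of panels". Section 10.5, for Visit 6, has "Late reactions are defined as reactions that initially occur at 7-10 days after application of the panels". Persistent needs first appearance at Day 2-4 in both sections. Section 10.5 allows no third class: "All reactions (scores of 1+, 2+ or 3+) will be categorized as either late or persistent". Section 10.4.2 has the same requirement.

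Protocol 13.6 lists active sensitization among the adverse events to be reported as related to the panels, and defines it as "A positive reaction initially appearing at approximately 21 days after application".

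SAP 5.2 contains two rules. One is AE duration. The other applies when Visits 4, 5 and 6 are all positive: if the scores at "visit 3 are doubtful or irritant then it will be considered as Positive (1+) at visit 3". Neither rule defines late or persistent. SAP 3.5 states that nothing in the analysis departs from the protocol, so the SAP inherits both windows.

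**The concern.** The investigator assigns the class at each visit, and the SAP tabulates frequencies. If the class is defined differently at Visit 5 and Visit 6, the same unchanged reaction can move between rows or drop out of the table. The outcome then depends on which section a site follows. If sites must choose one of two classes and neither fits, they will choose differently.

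What is at stake is how the Visit 6 rows can be read. A late count that mixes Day 7-14 reactions with first appearances around Day 21 combines two things that the protocol itself separates. The Visit 3 recode adds a further ambiguity, because the SAP does not say whether a recoded site keeps the class the investigator gave it.

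**Working it through.** The plan gives no figure to reproduce, so this is a comparison of definitions.

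**Inputs.** Visit windows (Protocol 10.3 to 10.5): Visit 3 is Day 3-4, Visit 4 is Day 7-8, Visit 5 is Day 10-14 and Visit 6 is Day 19-23. Late is onset on Day 7-14 in 10.4.2 and Day 7-10 in 10.5. Persistent is onset on Day 2-4 and still present later, in both sections.

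**Step 1: class by day of onset.**

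| Onset | Definition in 10.4.2 | Definition in 10.5 |
|---|---|---|
| Day 3-4 (Visit 3), still present later | persistent | persistent |
| Day 7-8 (Visit 4) | late | late |
| Day 10 (Visit 5) | late | late |
| Day 11-14 (Visit 5) | late | none |
| Day 19-23 (Visit 6) | none | none |

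Two rows fail. Onset on Day 11-14 is late when classified at Visit 5. If the reaction is still present at Visit 6, it has no class under the section that governs that visit. Onset on Day 19-23 has no class under either section, although both demand one.

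**Step 2: does the SAP resolve it?** SAP 4.2, 5.2, 6.2 and 7 were read for a rule. None names a window, a derivation, or a row for onset at Visit 6.

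**Step 3: the Visit 3 recode.** Take a site scored doubtful at Visit 3 and 1+ at Visits 4, 5 and 6.

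- By recorded scores, the first 1+ to 3+ is at Visit 4, which is late.
- After the SAP 5.2 recode, the first 1+ to 3+ is at Visit 3, which is persistent.
- The recode needs the Visit 6 score, so an investigator classifying at Visit 4 or 5 cannot know that it will apply.

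If the investigator coded late, the tables can show the site as 1+ at Visit 3 and as late at Visits 4 to 6. If the investigator took the doubtful reaction as the first appearance and coded persistent, the tables agree. The documents do not say which reading is intended.

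**Step 4: reach.** Protocol 10.6 counts a site as positive if any score at Visits 3 to 6 is 1+ to 3+. The late or persistent class does not enter that rule. The recode applies only where Visits 4, 5 and 6 are already positive, so it cannot change a site's overall positive status.

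**The case against.** The strongest reply is that the investigator assigns the class and the SAP need only count it. That is a workable plan, but the recorded code would still rest on two windows and on a forced choice with no valid answer for onset at Visit 6.

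A second reply is that the definitions speak of when a reaction first appears, not when it is first read. This stands. A reaction first read on Day 11-14 after a negative Visit 4 may have begun by Day 10. One first read at Visit 6 may have begun by Day 14 if Visit 5 fell early in its window. A reader might count the visit days without a class and infer how many reactions are affected. The documents do not support that: reading day is not onset day, and nothing is said about how first readings are distributed.

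A third reply concerns the recode. A doubtful or irritant score at Visit 3 can fairly be taken as a first appearance within Day 2-4, so persistent is a defensible code. This also stands. A reader might infer that every recoded site is misclassified, but the documents show only that the intended class is unstated.

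A reader might also infer that reactions first appearing at Visit 6, or late reactions that worsen, are lost to safety follow-up because the escalating code applies only to persistent reactions. That is not supported. Section 13.6 gives onset at about Day 21 an adverse event route, and its open-ended list includes severe cases of "Any characteristic associated with a late or persistent reaction (i.e. hyper-pigmentation, hypo-pigmentation, pruritus or other) at the test site" that last beyond the Day 21 evaluation. Sections 13.2 and 13.7 cover reporting and follow-up. What is missing is a table row.

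Finally, the table shells are a separate document (SAP section 9) and the data collection form is not provided. Either might hold a coding instruction, so the finding is limited to the protocol and SAP text.

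**Conclusion.** The point holds as a minor correction. The current protocol defines late in two ways and requires a class for reactions that can have none, and the SAP text does not choose between the windows or say how its Visit 3 recode bears on the class. Following the plan as written can give inconsistent late and persistent counts at Visit 6.

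The effect is on descriptive safety tabulation. How many reactions are touched cannot be derived from the documents. A reader might infer that dose selection is at risk, but Protocol 10.6 rules that out.

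The two conflicting definitions and the missing class for onset at Visit 6 can be read directly in current text and need no assumption. The recode element is weaker: it depends on how investigators treat a doubtful or irritant Visit 3 score, which the documents leave open.

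**What to change.** In SAP 5.2, before database lock, define the class by the visit of the first recorded 1+ to 3+ score. This avoids guessing onset between visits.

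- **Persistent:** first positive at Visit 3 and still positive at a later visit.
- **Late:** first positive at Visit 4 or 5, which is one Day 7-14 window used at every visit.
- **New at Visit 6:** first positive at Day 19-23, in its own row and cross-listed with active sensitization adverse events.
- **Not classifiable:** Visit 3 reading missing.

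Use recorded scores, without the Visit 3 recode, for this class and for the Visit 3 row of the safety tables. Both must follow the same rule: if the class uses recorded scores but the Visit 3 row keeps the recode, the mismatch in Step 3 remains. The alternative is to flag recoded sites in both places. List every recoded site, and list every site where the derived class differs from the investigator's code.

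At the next protocol amendment, change Day 7-10 to Day 7-14 in 10.5. This need not prompt an amendment of its own, because Protocol 8.3 requires approval from the authorities of six countries and from each ethics committee.

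The cost is one SAP definition, one derivation and short listings from scores already collected. No visit, procedure or form field is added. The derived class will differ from the investigator's code at some sites, and the listing shows where.

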10.5 Visit 6: Day 19-23

The investigative site will phone the subject to determine if there are any unresolved tape, polyester chip or allergen reactions at the test sites. If the subject reports no remaining reactions, the Investigator may choose at this point to complete the visit over the telephone.

- If the visit is conducted over the telephone all visit related paperwork including adverse events and/or changes to concomitant medications will be recorded.

Should the Investigator elect to see the subject in the office, the following procedures will be performed:

- Unresolved tape and or polyester chip induced irritation will be evaluated.
- Sites will be examined for the presence of erythema, infiltration, papules, discrete vesicles and bullous reactions and scored as follows: (-) negative, (1+) weak positive reaction, (2+) strong positive reaction, and (3+) extreme positive reaction.
- All reactions (scores of 1+, 2+ or 3+) will be categorized as either late or persistent. Late reactions are defined as reactions that initially occur at 7-10 days after application of the panels. Persistent reactions are defined as reactions that appear at day 2-4 and persist through day 7-21. Persistent reactions will be clarified as either persistent-healing or persistent-escalating. If a persistent-escalating reaction is noted at Visit 6, the investigator will determine required follow up action.
- Subject-reported adverse events, worsening of a pre-existing condition/disease/symptom or changes to concomitant medications will be recorded.
- De-identified photographs of site reactions may be taken at the discretion of the Investigator and will not be reviewed or collected by the study sponsor.

10.6 Post Visit 6

The Investigator will:

1. Evaluate tape or polyester chip induced irritation that increased in severity or persisted beyond visit 3. A potential allergic response may be considered if the skin response is consistent with criteria used to score 1+, 2+ or 3+ positive skin reactions according to standard patch testing guidelines established by the International Contact Dermatitis Research Group. The skin reaction must present with:
 - Palpable erythema, moderate edema or infiltrate, possibly few papules, no vesicles. Weak reaction (Score of 1+).
 - Strong infiltrate, numerous papules, possibly few vesicles present. Strong reaction (Score of 2+).
 - Coalescing vesicles, bullae or ulceration. Extreme reaction (Score of 3+).
2. Categorize the skin reactions at each site as either negative or positive. No skin reaction scores (1+, 2+ or 3+) assigned to during any of the reaction assessment visits, (Visits 3-6) would constitute a negative reaction. A positive skin reaction is defined as an assigned score of 1+, +2 or 3+ during at least one of the reaction assessment visits (Visits 3-6).

[figure not shown]
11.0 INVESTIGATIONAL PRODUCT IDENTITY AND USE

11.1 Investigational Allergen Panels

Investigational T.R.U.E. TEST panels are produced, packed and labeled by the manufacturer SmartPractice Denmark, in Hillerød, Denmark. To protect tests against light and air, panels are sealed in aluminum foil opaque pouches. Panels are to be stored under refrigeration at 2-8°C (36-46°F). Products are labeled with allergen batch codes and expiration dating.

[figure not shown]
Each investigational panel consists of a 5.2 x 13.0 cm piece of surgical tape containing as many as 12 allergen patches. Although each allergen patch is assigned a 'chip number' for product identity, scoring will be by position placement as illustrated below.

Figure 7: Illustration of Position Numbering

An up arrow and two notches indicate the proper product orientation. The uppermost notch on the left side of the panel indicates the top left of the panel, the lower notch indicates the bottom of the panel. The patch chip numbering is unmistakable when the panel is removed from its pouch. Panels are to be applied with the numbers facing upright.

Figure 8: Application of Dilution Series Allergens

- Peel open package and remove test panel.
- Remove plastic covering.
- Position the panel to the paraspinal region of the upper back being careful to avoid areas of contact dermatitis, uneven skin tones, tattoos, scars, moles, excessive hair or other skin disfigurement.
- Ensure that each patch is in contact with the skin by smoothing the panel outward from the center
- Use a skin marker to indicate the location of the two notches on the panel
- Panel may be secured with additional tape, if needed.

[figure not shown]
In order to differentiate between panels once they are applied the following chip numbers are used for each panel. The *set* of numbers used is unique to each panel so that individual panels can easily be identified:

	Panel 1	Panel 2	Panel 3	Panel 4	Panel 5	Panel 6
Chip numbers	1-4 and 7-10	13-24	25-28 and 31-34	25-36	3-6 and 9-12	1, 4, 5, 7, 8, 12, 28

The lead chemist in the department of pharmaceutical development at SmartPractice Denmark is responsible for the randomization of allergens on panels 1-5. The allergens will be randomized within each panel into three different configurations, per standard protocol. The different allergen configurations will be randomly assigned to subjects as they enter the study. The investigators and subjects will be aware of the allergens and the patch test doses on the test panels but will not be aware of the placement of the allergens on the individual panels (the different panel configurations). The key to the randomization scheme will be kept confidential at SmartPractice Denmark until it is forwarded to data management for analysis of the study results following completion of all study related procedures.

The allergens on panel 6 will not be randomized into different configurations. Should the Investigator elect to omit the common allergens from an individual's patch testing, the panel should be cut as shown below in Figure 9.

Figure 9: Panel 6 Configuration and Cutting Instructions

Unused portion of the panel is not to be discarded.

The remaining portion of the panel must be applied as it contains the excipient and blank patch controls. Scores for the blank (Position 4), PVP (Position 8), and HPC (Position 9) patches will be recorded in the case report forms as originally intended, in fields for positions 4, 8 and 9. Positions 1, 2, 3 and 7 will be documented in the case report form as 'not applied'.

All investigational products used in this study must be accounted for. Records must show amount and date of delivery of all test materials to the investigator. Likewise dates, amount, and signatures should document return of unused test panels. Product deliberately and/or accidentally destroyed by the investigator must also be documented.

The use of the investigational product for the individual subject, including number and identification of specific panels applied, application (or not) of common allergens and date and time of application and removal will be documented.

The following investigational panels with ascending doses of allergen and an excipient control will be used in this study.

Panel 1 Aluminum Dilution Series

Allergen	Excipients	Ascending Dosages (mg salt/cm ²)	Randomized Among Positions
Aluminum chloride hexahydrate	Water, Ethanol (99.9%), PVP	0.040, 0.12, 0.36, 0.72	1-4 and 7-10
Aluminum lactate	Water, Ethanol (99.9%), PVP	0.047, 0.14, 0.42, 0.84	

Panel 2 Copper, Zinc and Tin Dilution Series

Allergen	Excipients	Ascending Dosages (mg salt/cm ²)	Randomized Among Positions
Copper sulfate anhydrous	HPC, Water	0.013, 0.040, 0.080, 0.12	1, 2 and 7, 8
Zinc chloride	HPC, Water	0.013, 0.040, 0.080, 0.24	3, 4 and 9, 10
Tin chloride dihydrate	HPC, Water, Ethanol	0.018, 0.037, 0.11, 0.33	5, 6 and 11, 12

Panel 3 Manganese and Molybdenum Dilution Series

Allergen	Excipients	Ascending Dosages (mg salt/cm ²)	Randomized Among Positions
Manganese chloride	HPC, Water	0.013, 0.040, 0.080, 0.24	1-4
Ammonium molybdate	HPC, Water	0.0067, 0.020, 0.040, 0.12	7-10

Panel 4 Titanium Dilution Series

Allergen	Excipients	Ascending Dosages (mg Ti/cm ²)	Randomized Among Positions
Titanium peroxo citrate	PVP, Water	0.055, 0.11, 0.22	1-12
Titanium lactate	PVP, Ethanol	0.070, 0.14, 0.28	
Potassium titanium oxide oxalate	PVP, Ethanol	0.060, 0.12, 0.24	
Ammonium titanium oxide oxalate	PVP, Water	0.055, 0.11, 0.22	

Panel 5 Vanadium Dilution Series

Allergen	Excipient	Ascending Dosages (mg V/cm ²)	Randomized Among Positions
Vanadium chloride	HPC, Water	0.0042, 0.0083, 0.025, 0.050	1-4 and 7-10
Vanadium oxide sulfate	HPC, Water	0.0042, 0.0083, 0.025, 0.050	

Panel 6 Common Allergens/Excipient Controls

Allergen/Control	Excipient	Dose (mg/cm ²)	Position
Nickel sulfate	HPC	0.20	1
Potassium dichromate	PVP	0.054	2
Gold sodium thiosulfate	HPC	0.075	3
Blank Patch Negative Control	None	NA	4
Cobalt dichloride	HPC	0.020	7
PVP Negative Control	PVP	NA	8
HPC Negative Control	HPC	NA	9

The dose per unit area of experimental T.R.U.E. Test allergens is calculated based on the molecular weight of the compound. Exceptions are Titanium and Vanadium allergens as molecular weights are not known for all of these, hence the dose per unit area for Titanium and Vanadium allergens is based only on the metal part of the compound.

